4.1.2. Dose-Limiting Toxicity

The DLT observation window will be 21 days (1 cycle). Any participant that received at least 1 dose of belantamab mafodotin will be evaluated for DLTs using NCI-CTCAE Version 5.0 [NCI, 2017]. If participants prematurely discontinue for reasons other than toxicity but prior to completion of DLT observation period, additional participants may be enrolled as replacement participants at the discretion of the Sponsor in consultation with the investigator.

An event will be considered a DLT if its relationship to the investigational agent cannot be ruled out, occurs within the DLT reporting period and meets 1 of the following criteria:

- a. Any Grade 3 or greater non-hematologic toxicity as described in NCI-CTCAE Version 5.0 [NCI, 2017], other than corneal events:
- Persists for >48 hours despite supportive treatment
- Leads to hospitalization
- b. Haematologic toxicity:
- Grade 3 or greater febrile neutropenia lasting >48 hours despite adequate treatment:
 - Grade 3 CCI
 Grade 4 CCI
 CCI This section contained Clinical Outcome Assessment data collection questionnaires or indices, which are protected by third party copyright laws and therefore have been excluded.
- Grade 4 thrombocytopenia
 CCI
 CCI
- c. Grade 4 per the modified corneal grading scale provided in Table 7.
- d. Liver toxicity meeting pre-specified GSK liver stopping criteria as outlined in Section 7.1.1.

A participant who develops a DLT will be allowed to continue study treatment if the toxicity did not meet pre-defined stopping criteria (Section 7.1)and recovered to Grade ≤1 within 14 days or after a longer recovery period if the investigator and medical monitor agree that for a given participant the potential benefits may outweigh the risks.

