6.6. Dose Modification

Table 4 details the permitted dose modifications of belantamab mafodotin. Table 5 and Table 6 contain dose modification guidance for drug-related AEs. See Table 7 for dose modification guidelines for belantamab mafodotin treatment-related changes in vision.

Table 4 Permitted Dose Reductions

Starting dose	Dose reduction
2.5 mg/kg	1.9 mg/kg
3.4 mg/kg	2.5 mg/kg, 1.9 mg/kg

If the participant cannot tolerate the drug after the allowed dose reduction of belantamab mafodotin to the lowest allowed dose of 1.9 mg/kg, he or she must discontinue treatment for lack of tolerability.

In case of full resolution of symptoms which lead to dose reduction, further treatment at the previous dose level may be considered by the investigator.

If a dose is delayed, the participant should wait for the next scheduled dose to resume treatment. In individual cases where in the judgment of the Investigator waiting a full cycle to resume treatment after delay (skipping dose) related to toxicity which has resolved would be detrimental to the participant's health, the PI should contact the Medical Monitor to discuss an earlier re-start. An earlier re-start may be considered only for participants who have recovered from toxicity to at least ≤Grade 1. The dosing with belantamab mafodotin cannot occur more frequently than every 21 days (±3-day

window). In such cases, efficacy and safety assessments must remain every 3 weeks in line with initial efficacy and safety assessments on study, which may result in 2 separate visits (1 for dosing, 1 for disease assessments). Evaluations associated with a dose would be entered into the eCRF under the next scheduled cycle.

Resuming treatment with belantamab mafodotin will be possible with or without dose reduction after the toxicity has resolved to Grade 1 or less.

Table 5 Dose Modification Guidelines for Belantamab Mafodotin-Related Adverse Events

Toxicity	Grade/description of toxicity	Recommendations for Belantamab Mafodotin
Elevated serum creatinine which cannot be explained by concomitant sepsis, TLS, other severe condition with fever, or dehydration	If absolute serum creatinine increases from baseline by >0.5 mg/dL	 Repeat serum creatinine within 48 hours If confirmed: withhold therapy, institute treatment and monitoring as clinically indicated, and follow for resolution Discuss any further dosing with Medical Monitora

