Serum creatinine >Grade 3 or absolute increase by 3 mg/dL	>3.0 mg/dL from baseline or 3.0xULN	 Provide appropriate medical treatment. Permanently discontinue treatment with belantamab mafodotin
Spot urine (albumin /Creatinine ratios)	>2000 mg/g (or 224 mg/mmol)	 Re-test (at least 7 days apart). If not confirmed, continue belantamab mafodotin at current dose If confirmed on re-test and no clear evidence of disease progression Interrupt treatment with belantamab mafodotin Repeat testing within 4 weeks If spot urine <2000 mg/g (224 mg/mmol), may restart belantamab mafodotin with dose reduction If spot urine remains >2000 mg/g (224 mg/mmol) after 4 weeks, permanently discontinue belantamab mafodotin and withdraw participant from study; provide treatment as clinically indicated and follow for resolution^a
Urine Dipstick	2+	 May continue belantamab mafodotin dosing Confirm by quantitative assessment using albumin/creatinine (spot urine from first void) If albumin/creatinine >2000 mg/g, at the next cycle follow guidance above for Spot Urine.
	3+	Interrupt treatment and follow up for recovery. Implement quantification of albumin/creatinine ratio
Thrombooytopenia	Grade 3	 No bleeding: continue treatment with 1 dose level reduction. Consider reverting to previous dose once thrombocytopenia recovered to Grade 2 or less With bleeding: withhold the dose, continue treatment after recovery with 1 dose level reduction Consider additional supportive treatment (e.g., transfusion), as clinically indicated and per local practice.
Thrombocytopenia (on days of dosing)	Grade 4	Withhold the dose. Consider restarting with 1 dose level reduction if recovered, or transfused to ≤Grade 3 only if there is no active bleeding at time of treatment restart If thrombocytopenia is considered disease related, is not accompanied by bleeding, and recovers with transfusion to >25x109/L continuing treatment at 1 dose level reduction may be considered after discussion with the Medical Monitor

Toxicity	Grade/description of toxicity	Recommendations for Belantamab Mafodotin
Febrile neutropenia	Defined as: single temp of 38.3°C, or sustained 38°C for >1 h AND ANC <1.0×109/L	 Withhold belantamab mafodotin and immediately hospitalize participant with appropriate management, per local institutional guidance. Consider additional supportive treatment per local practice (e.g. growth factors). Upon recovery, consider a dose reduction of belantamab mafodotin, if neutropenia was drugrelated.

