Grade 2	 Administer symptomatic treatment Investigate etiology Consider consulting subspecialist, and/or diagnostic procedure 	 Symptoms resolved in ≤7 days: Continue after resolution at the current dose Symptoms ongoing >7 days or worsening: Delay study drug, or consider dose reduction by 25% If recovery takes >3 weeks- consult GSK MM If symptoms continue or worsen to Grade 3-4, see below
Grade 3	 Provide appropriate medical treatment Consider Consulting subspecialist 	 Delay study treatment till recovery to G1 or less. Consider dose reduction. Consider consultation with GSK MM. Exceptions: Participants who develop G3 toxicities which respond to standard treatment and resolve to ≤G1 within 48 hours may continue treatment at scheduled or reduced dose
Grade 4	 Provide appropriate medical treatment Consider consulting subspecialist Discuss with Sponsor/Medical Monitor 	 Interrupt treatment. Further study treatment with belantamab mafodotin only allowed on individual basis if in the discussion with MM it is agreed that benefits outweigh the risks for a given participant

Treatment-related decisions can be made based on local laboratory results if central results are not available or delayed.

Table 7 Dose Modification Guidelines for Belantamab Mafodotin Treatment-Related Changes in Vision

Grade/description of toxicity (as described in NCI-CTCAE ver. 5.0)	Recommendations
CCI - This section contained Clinical Outcome Assessment data collection questionnaires or indices, which are protected by third party copyright laws and	Continue treatment at current dose.
therefore have been excluded.	Dose reduce by 25% (either to 2.5 or to 1.9 mg/kg) and continue treatment.
	If already on 1.9 mg/kg, participant continues treatment at same dose.
	Upon resolution (e.g., Grade 1), re-escalation to previous dose may be considered.
	Hold treatment and allow to recover to Grade ≤2.
	Once recovered, dose reduce to 2.5 or to 1.9 mg/kg.
	If already on 1.9 mg/kg, participant continues at same dose.
	If after event resolution eye symptoms are considered stable for at least 3 cycles and if vision is Grade ≤1, consider re-escalation (to 3.4 or 2.5 mg/kg).
	Hold treatment and allow to recover to Grade ≤2.
	Restart only after discussion with Medical Monitor for participants whose vision improves to Grade ≤2. If restart approved, once recovered to Grade ≤2, dose reduce to 2.5 or 1.9 mg/kg. If already on 1.9 mg/kg, participant continues at same dose.

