9.5.2. Dose Escalation Committee (DEC)

The Dose Escalation Committee (DEC) will monitor intervention-emergent data on an ongoing basis throughout study conduct for the purpose of ensuring the continued safety

of participants enrolled in this study as described in the Dose Escalation Plan. The DEC will be chaired by the GSK medical monitor and membership will include a GSK clinical scientist, GSK safety physician, GSK statistician, GSK pharmacokineticist, along with additional GSK staff as appropriate and all participating investigators.

The DEC will review of relevant safety, PK, and PD data generated immediately after all participants treated in the same dose cohort have passed the DLT period.

Dose Escalation Meetings will be scheduled at the conclusion of the DLT assessment period for participants enrolled in each cohort to review safety data and determine the next dose level appropriate for study.

In addition, throughout the conduct of the study the DEC may decide to:

- 1) Modify the dose escalation of belantamab mafodotin proposed by the 3+3 model based on clinical judgement.
- 2) Investigate alternative dosing regimens
- 3) Modify the timing, frequency, and/or type of safety assessments performed during study conduct
- 4) Approve continuation of belantamab mafodotin study therapy in participants who have experienced DLT provided the toxicity did not meet study discontinuation criteria and has resolved at the time of re-start.
- 5) Request intervention of additional participants at previously completed dose levels for the purpose of obtaining additional safety, PK, PD, metabolite, or biomarker data (i.e. PK/PD/Metabolite).
- 6) Halt enrolment into any cohorts as deemed appropriate based on emerging clinical data at any time during the trial.

Dose escalation decisions will be made with DEC members after review of available safety data from at least one cycle of therapy with belantamab mafodotin. Available data will be provided to participants prior to each scheduled Dose Escalation Meeting. Attendees of Dose Escalation Meetings will include but not limited to DEC members. All dose escalation and safety decision will be documented in writing with copies maintained by GSK in the Trial Master File and submitted to each site for documentation. Decisions with potential impact on the safety of study participants (i.e., unfavorable change in risk/benefit assessment) will be promptly communicated to regulatory authorities and study sites as appropriate.

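### Restart thresholds in Protocol Sections 6.6 and 4.1.2 contradict Tables 5 and 7 with no statement of which prevails, and the instructions at 1.9 mg/kg are neither reconciled nor complete

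*Protocol*

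**What the plan says.** **General rule.** The Section 6.6 text between Tables 4 and 5 reads: "Resuming treatment with belantamab mafodotin will be possible with or without dose reduction after the toxicity has resolved to Grade 1 or less". It carries no exception for toxicities that have their own table row.

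**After a DLT.** Section 4.1.2 allows a participant to continue if no stopping criterion was met and the toxicity "recovered to Grade ≤1 within 14 days or after a longer recovery period if the investigator and medical monitor agree". Its DLT criteria include Grade 4 on the Table 7 corneal scale and Grade 4 thrombocytopenia; text next to the latter is redacted.

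**Table 5.** Neutropenia of Grade 3 or more is resumed at the dose given before the hold once it reaches Grade 2 or less on Day 1 of the next cycle. For Grade 4 thrombocytopenia: "Consider restarting with 1 dose level reduction if recovered, or transfused to ≤Grade 3 only if there is no active bleeding".

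**Table 7 (vision).** The hold rows say: "Hold treatment and allow to recover to Grade ≤2". At the lowest dose: "If already on 1.9 mg/kg, participant continues treatment at same dose"; the hold rows say the same in slightly different words.

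**Floor, general text.** Section 6.6 says that if the participant cannot tolerate the drug after reduction "to the lowest allowed dose of 1.9 mg/kg, he or she must discontinue treatment for lack of tolerability".

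**Who decides.** Section 4.1.2 names the investigator and medical monitor (for a longer recovery). Section 7.1.3 sends Grade 4 ocular events to the Medical Monitor. Section 9.5.2 lets the DEC approve continuation after a DLT, "provided the toxicity did not meet study discontinuation criteria and has resolved at the time of re-start".

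**The concern.** A site that needs to know whether it may redose a participant can find two answers. Under one passage the participant is eligible; under another the toxicity has not recovered far enough. At 1.9 mg/kg one passage mandates stopping and another mandates continuing, depending on how tolerance is judged.

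What is at stake is first the safety of redosing. The rules are still in use, because the current amendment extends the study for two participants who remain on treatment. Second, the choice of passage changes planned outputs: dose delays and reductions (SAP 6.5), action taken for corneal events and thrombocytopenia (SAP 8.3), AEs leading to discontinuation or dose modification (SAP 8.5), and eligibility for the accumulation ratios, which require early cycles without delay or dose change (SAP 10.3.1.2).

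**Working it through.** No calculation tests this point. The check sets the passages side by side.

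| Situation | Tables | General text of 6.6 | 4.1.2, if the event was a DLT |
|---|---|---|---|
| Neutropenia, recovered to Grade 2 on Day 1 of the next cycle | Table 5: resume, same dose | Grade 1 not reached | – |
| Grade 4 platelets on a dosing day, transfused to Grade 3, no bleeding | Table 5: restart one level lower may be considered | Grade 1 not reached | Grade 1 not reached |
| Grade 4 corneal event, recovered to Grade 2 | Table 7: restart possible after Medical Monitor discussion | Grade 1 not reached | Grade 1 not reached |
| Vision event calling for a reduction, or a hold and recovery, on 1.9 mg/kg | Table 7: continue at the same dose | Discontinue, if the event is read as not tolerating the drug | – |
| Grade 3 or 4 thrombocytopenia on 1.9 mg/kg | Table 5: reduce one level; Table 4 has no lower level | Discontinue, on the same reading | – |

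**Is there a precedence rule?** None was found. Only Table 6 is marked as residual, for events not otherwise specified. The general text of 6.6 has no such label.

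**Does the longer-recovery clause of 4.1.2 remove the DLT conflict?** It reads most naturally as extending the 14 days, not as relaxing Grade 1. The sentence is loosely built, which is a further reason to reword it.

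**Can Grade 1 always be reached?** Eligibility admits a neutrophil count of 1.0 × 10⁹/L or more, which Table 5 equates with Grade 2 or less. A participant may therefore enter at Grade 2 and be unable to meet a Grade 1 restart rule.

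**Floor branch.** The Grade 2 pneumonitis row of Table 5 says what to do at 1.9 mg/kg; the thrombocytopenia rows do not. Section 4.1.1 also permits a de-escalation cohort at 1.9 mg/kg, and Table 4 has no row for that starting dose.

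**Where there is no conflict.** Grade 3 infusion reactions use Grade 1 or less in Table 5 as well. Rows that order permanent discontinuation are consistent with 4.1.2, because Section 7.1 counts the 6.6 stopping rules among the stopping criteria.

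**Weight of one participant.** If six are treated in a cohort, one classified differently moves a percentage by 1/6 = 16.7 points; with three, by 1/3 = 33.3 points.

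**The case against.** The best defence is that a toxicity's own row governs and the general sentence covers the rest. Section 6.6 opens by sending the reader to the tables, and its general sentence says that resuming is possible after Grade 1, not only then; the preceding paragraph does write the restriction explicitly for early re-start. This is a sensible reading, but the protocol does not state it. Nor does it settle 4.1.2 against the tables, since the DLT rule is itself specific, and it supplies no floor branch for thrombocytopenia.

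Other objections stand and limit the point:

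- A reader might infer that a DLT faces three incompatible restart rules. The documents do not support that. The DEC provision is a power to approve, and its wording sets no rival grade. Section 7.1.3 already gives Grade 4 ocular events a route, and the DEC is chaired by the medical monitor and includes the investigators. What is missing is how these routes fit together.
- A reader might infer that this is the common case from the protocol's 2.5 mg/kg figures: thrombocytopenia 38%, keratopathy 71%, delays 51%, reductions 32%. The first covers Grades 1 to 4, the second includes findings without symptoms, and the last two cover all AEs. None counts the held events at issue.
- A reader might set the 14 days of 4.1.2 against corneal resolution times of 21 to 201 days (median 91) and conclude that the route can never be met. Those times are for findings of Grade 2 or above, and the same sentence allows longer recovery. Onset was at a median of 36 days (range 19 to 143) against a 21-day DLT window, so on these figures few corneal DLTs would be expected.
- A reader might infer that a 2.5 mg/kg starter, with one reduction step, meets the floor conflict at the second event. That follows only if a recovered event counts as not tolerating the drug, which is undefined.
- Table 5's Grade 4 thrombocytopenia row applies on dosing days, so it meets the DLT rule only if the event persists to one.

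**Conclusion.** The point holds as a contradiction between stated rules. The Grade 1 wording of 6.6 and 4.1.2 cannot be reconciled with Grade 2 (neutropenia and Table 7) or Grade 3 (thrombocytopenia) without a precedence rule that the protocol lacks. The floor problem is narrower: a possible conflict that turns on an undefined term, plus a definite gap in the thrombocytopenia rows.

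Its size cannot be put as a rate. It does not alter which Cycle 1 events count as DLTs. With 3.4 mg/kg optional and the amendment written around two ongoing participants, the DLT limb probably matters only if a cohort opens or reopens; the general restart and floor rules apply to anyone still dosed.

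Two assumptions remain. The redacted text beside the thrombocytopenia DLT criterion is taken not to remove the overlap. The Table 7 row requiring Medical Monitor discussion is taken to be Grade 4, which Section 7.1.3 suggests but the redaction hides. The restart thresholds and floor instructions themselves are visible.

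**What to change.** Reconcile Section 4.1.2, the general text of 6.6, Tables 4, 5 and 7, Section 7.1.3 and Section 9.5.2:

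- Give each toxicity one restart threshold and one decision route, used identically wherever it appears; or state in both 6.6 and 4.1.2 which passage prevails. A sentence in 6.6 alone would leave the DLT conflict open.
- Say how the investigator and Medical Monitor decision relates to DEC approval after a DLT.
- Define what counts as not tolerating the drug, and align the discontinuation sentence in 6.6 with Table 7.
- Complete the thrombocytopenia rows for a participant with no reduction left, and cover a 1.9 mg/kg starting dose in Table 4.

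Which threshold or action applies is the sponsor's clinical decision. The cost is protocol wording and the ethics approval that any amendment needs under Appendix 1; there are no extra visits, participants or analyses.

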- 3. Belantamab mafodotin will be administered intravenously on Day 1 (D1) of every 21-day cycle until disease progression, death, unacceptable toxicity, withdrawal of consent or end of study.
- 4. The End of treatment (EOT) follow-up visit is to assess any residual AEs or toxicities associated with Study treatment. The visit should occur -within 45 days after last dose or before the start any new anti-cancer therapy.
- 5. PD follow-up once every 21 days: Participants who discontinue IP for a reason other than PD, disease evaluations will continue to be performed once every 21 days (±7 days) until confirmed PD, death, start of a new anticancer treatment, withdrawal of consent, or end of the study whichever occurs first.
- 6. Screening examination will be performed by an ophthalmologist (or an optometrist if an ophthalmologist is not available) within 21 days prior to first dose. See Section 8.3.9 for the list of ophthalmic exam procedures.
- 7. On-study ophthalmic exams to be performed by an ophthalmologist (or an optometrist if an ophthalmologist is not available) pre-dose every 3 weeks (schedule of assessment window should be within 5 days prior to dosing, all efforts should be made to schedule as close to dosing as possible). After the 6th dose of belantamab mafodotin (no schedule of assessment window needed): If there are no significant (Grade 2 or above) ocular symptoms or vision changes the frequency of ophthalmologic exams may be decreased to every 3 months until end of treatment. In case of persistent ocular exam findings, newly developed ocular symptoms or vision changes, further ocular exams should be performed at least every cycle until resolution (to Grade 1 or baseline) or more frequently as clinically indicated by the qualified eye care specialist (Appendix 9). See Section 8.3.9 for the list of ophthalmic exam procedures
- 8. Additional exams may be performed by the ophthalmologist (an optometrist if an ophthalmologist is not available), as clinically indicated.
- 9. If a participant's belantamab mafodotin dose is not administered at a given visit, the following activities do not need to be performed at that visit unless clinically indicated: ECG, weight, vitals, pregnancy test. Please follow the visit schedule in the SOA above, and perform these activities prior to a belantamab mafodotin infusion

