Neutropenia	Grade ≥3 Defined as ANC <1.0x10 ⁹ /L	 If noted on Day 1 of any cycle, withhold belantamab mafodotin. Consider more frequent hematology (CBC) monitoring as clinically indicated, until recovery to Grade 2 or less. Resume belantamab mafodotin at pre-held dose once neutropenia recovers to Grade ≤ 2 (ANC ≥ 1.0x10⁹/L) on Day 1 of the subsequent cycle. Prophylactic antibiotics, per physician discretion and local institutional guidance. Consider growth factors. Local guidance must be followed for hematological monitoring, if more conservative than the protocol SoA specifications. In cases of frequent recurrent neutropenia (ANC <1.0x10⁹/L), consider dose reduction of belantamab mafodotin by 1 level
	2	Stop the infusion, provide medical treatment and continue at half the original infusion rate after resolution to Grade 0-1. Any future infusion needs to be pre-medicated.
Infusion Reaction ^b	3	 Further treatment with belantamab mafodotin needs to be discussed with Medical Monitor. Continuation only allowed after recovery to ≤Grade 1 and with pre-medication, and extension of infusion time to 2-4 hours. Any future infusion needs to be pre- medicated.
	4	Permanently discontinue from study treatment
Pneumonitis	2	 Withhold treatment with belantamab mafodotin Upon recovery, restart treatment with 1 dose level reduction. If patient is already at the lowest dose level (1.9 mg/kg), then rechallenge with the same dose must be discussed with the Medical Monitor
	Grade 3-4	Permanently discontinue from treatment

a. Medical Monitor may consult GSK's nephrotoxicity panel about plans to continue therapy.

b. If symptoms resolve within one hour of stopping infusion, the infusion may be restarted at 50% of the original infusion rate (e.g., from 100 mL/hr to 50 mL/hr). Otherwise dosing will be held until symptoms resolve and the participant must be pre-medicated for the next scheduled dose.

Table 6 General Dose Modification and Management Guidelines for Drugrelated Adverse Events Not Otherwise Specified

Severity	Management	Follow-up
Grade 1	 Administer symptomatic treatment as appropriate Continue study drug(s)^a 	Provide close follow-up to evaluate for increased severity, no dose modification necessary

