7. DISCONTINUATION OF STUDY TREATMENT AND PARTICIPANT DISCONTINUATION/WITHDRAWAL

7.1. Discontinuation of Study Treatment

Participant will receive study treatment until disease progression, death or unacceptable toxicity (including but not restricted to meeting stopping criteria for significant toxicity as outlined in Section 6.6), loss to follow-up, or end of study (Section 4.4).

The study treatment must be permanently discontinued for any of the following reasons:

- disease progression or unacceptable toxicity (including protocol-defined safety stopping criteria)
- Pregnancy

Study treatment may be permanently discontinued for any of the following reasons:

- deviation(s) from the protocol
- request of the participant or proxy (withdrawal of consent by participant or proxy)
- Investigator's discretion
- concurrent illness that prevents further administration of study treatment(s)
- participant is lost to follow-up

study is closed or terminated.

The primary reason of study treatment was permanently discontinued must be documented in the participant's medical records and electronic case report form (eCRF).

If the participant voluntarily discontinues from treatment due to toxicity, AE must be recorded as the primary reason for permanently discontinuation on the eCRF.

Once a participant has permanently discontinued from study treatment, the participant will not be allowed to re-enter the study.

All participants who discontinue from study treatment for any reason other than confirmed progression or death will complete safety assessments, and will be followed up for PD after study as specified in the SoA (Table 1).

PD Follow-up:

All participants who permanently discontinue study treatment in the absence of disease progression will remain in the study and will be followed for progression according to the protocol schedule until:

- Progression is documented, or
- New anti-cancer therapy is initiated, or
- Lost to follow-up, or
- Withdrawal of consent, or
- Death occurs, or
- End of study (Section 4.4)

[figure not shown]

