7.1.2. Allergic and Anaphylactic Reaction Stopping Criteria

All participants will be monitored carefully for evidence of allergic response. A participant that exhibits signs or symptoms of severe hypersensitivity or anaphylaxis will receive appropriate medical treatment and permanently discontinue study treatment but will continue in the study.

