7.1.4. Infusion-Related Reaction Stopping Criteria

Premedication is not required prior to infusion unless deemed medically appropriate by the investigator following evaluation of IRRs. Premedication should be considered in any participant who experienced an IRR at first or any subsequent infusion with belantamab mafodotin.

Infusion related reactions should be managed by guidelines provided in Table 5. A participant that experiences a Grade 4 IRR must permanently discontinue study treatment but will continue in the study.

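### Table 5 withdraws a participant from the study for persistent albuminuria without progression, which contradicts Section 7.1 and Schedule footnote 5; Section 4.1 adds to the conflict

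*Protocol*

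**What the plan says.** Protocol Section 6.6, Table 5 (spot urine row) covers a ratio above 2000 mg/g. The site re-tests at least 7 days later. If the value is confirmed and there is no clear evidence of progression, the site interrupts treatment and repeats the test within 4 weeks. If the ratio is still above 2000 mg/g after 4 weeks, the site is to "permanently discontinue belantamab mafodotin and withdraw participant from study", then treat as indicated and follow for resolution. The 2+ entry of the dipstick row leads to the same guidance when the ratio exceeds 2000 mg/g, so there are two routes in.

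Section 7.1 says: "All participants who permanently discontinue study treatment in the absence of disease progression will remain in the study and will be followed for progression". Its list of events that end this follow-up is progression, new anti-cancer therapy, loss to follow-up, withdrawal of consent, death or end of study. Toxicity is not on it.

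Schedule of Activities footnote 5 says: "Participants who discontinue IP for a reason other than PD, disease evaluations will continue to be performed once every 21 days".

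Section 4.1, repeated in SAP Section 2.3, describes each participant's involvement as lasting until progression, death, withdrawn consent, loss to follow-up or treatment discontinuation for other reasons.

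**The concern.** A site with such a participant meets two instructions that cannot both be followed, and no text sets precedence or exempts the renal case. The nephrotoxicity row of the risk table in Section 2.4.1 sends the site to both Section 6.6 and Section 7.1.

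Taken literally, the Table 5 cell ends three things for someone whose albuminuria is unresolved:

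- **Scheduled progression assessments.** These feed the descriptive duration of response (Protocol Section 9.4.9; SAP Section 7.2).
- **Dipstick and creatinine at PD follow-up visits.** Both are scheduled there (Schedule dipstick row; footnote 11).
- **Collection of related SAEs through PD follow-up** (footnote 36).

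Sites that resolve the conflict differently would also record study withdrawal differently, and SAP Section 6.2 tabulates withdrawal by reason.

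**Working it through.** The plan states no figure on this point, so the check is mainly a comparison of texts, with short arithmetic on timing.

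**1. Permanent stops in Table 5**

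| Toxicity | Instruction | Orders study withdrawal? |
|---|---|---|
| Serum creatinine | "Permanently discontinue treatment with belantamab mafodotin" | No |
| Spot urine ratio | "permanently discontinue belantamab mafodotin and withdraw participant from study" | Yes |
| Infusion reaction, Grade 4 | "Permanently discontinue from study treatment" | No |
| Pneumonitis, Grade 3-4 | "Permanently discontinue from treatment" | No |

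One of four entries orders withdrawal, and it does so as a second act after stopping the drug.

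**2. Stopping rules outside Table 5.** For severe hypersensitivity or anaphylaxis, Section 7.1.2 has the participant "permanently discontinue study treatment but will continue in the study". For a Grade 4 infusion reaction, Section 7.1.4 says the participant "must permanently discontinue study treatment but will continue in the study". Section 4.4 lists when a participant counts as withdrawn, and toxicity is not listed.

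**3. Effect on the DLT endpoint.** The shortest path from the first high ratio to withdrawal is 7 + 28 = 35 days. The DLT window is 21 days, so withdrawal falls after it.

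**4. Effect on ORR.** Section 8.1 keeps assessments on the calendar schedule during a dose hold. Within 35 days, floor(35/21) = 1, so at least one scheduled response assessment occurs before withdrawal. The Schedule also marks a response assessment at the end-of-treatment visit. Under SAP Table 1, row 11, a response becomes not evaluable if no adequate assessment follows because the participant discontinued the study. That requires the response to be first seen at the participant's final assessment.

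**5. PD follow-up visits inside the 70-day adverse event window.** Assume visits every 21 days from the discontinuation decision, ignoring the ±7-day window.

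- Clock starts at the decision: 70/21 = 3.33, so 3 visits (days 21, 42, 63).
- Clock starts at the last infusion, given on the day of the first high ratio: the decision comes at day 35 at the earliest, leaving 70 − 35 = 35 days, and floor(35/21) = 1.
- As above, but the dose was held at that visit, so the last infusion was 21 days earlier: 70 − 35 − 21 = 14 days, giving 0.
- Limiting case, with an infusion on the day of the confirming re-test: 70 − 28 = 42 days, giving at most 2.

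Protocol Section 8.3.1 counts from discontinuation of study treatment and SAP Section 14.4.1 from the treatment stop date. Neither settles which start applies after a long hold.

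**6. What each lost visit carries.** One response assessment, one dipstick and one creatinine. The albumin/creatinine ratio itself is not scheduled at PD follow-up visits.

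**The case against.** **Section 4.1 agrees with Table 5.** On its words, any treatment stop for other reasons ends that participant's involvement. This stands as a second conflicting text, so the Table 5 cell is not a lone outlier. It does not reconcile the protocol: read as an individual exit rule, it would leave Section 7.1's PD follow-up, footnote 5 and the Schedule's PD follow-up column with almost no one to apply to.

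**The wording may be loose.** The hepatotoxicity row in Section 2.4.1 says participants who meet liver stopping criteria will be withdrawn from the study, while Section 7.1.1.1 stops treatment and allows continued follow-up. The disputed cell itself ends by asking for follow-up to resolution, and it sits under a column headed as recommendations for the drug. A sensible site may therefore read it as a treatment stop. That is fair, but the cell has already stopped the drug before it adds withdrawal.

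**Section 7.2 permits withdrawal for safety.** It does so at the investigator's discretion. Table 5 makes withdrawal the instruction.

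**Other duties cover much of the loss.** This largely stands. Section 8.3 keeps the investigator responsible for following adverse events that are serious, related or led to stopping treatment. Section 8.2.5 requires clinically significant abnormal laboratory tests, during participation or within 30 days of the last dose, to be repeated until they settle. Section 8.3.1 keeps the 70-day window and the duty to notify related SAEs learned of after discharge. Section 7.2 asks for an early discontinuation visit if possible.

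**Conclusion.** The contradiction is real and is wrong as written, not a design choice. Its severity is minor. What is actually lost is scheduled progression follow-up, which cuts short the observation behind a descriptive DOR that is not a listed primary or secondary endpoint, together with the dipstick, creatinine and related-SAE collection tied to those visits.

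Three stronger readings are tempting and are not supported:

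- **Renal safety monitoring stops.** It does not; the duties listed above continue.
- **ORR could move materially.** In a cohort of 6, one lost response would be 1/6 = 16.7 percentage points, but this ignores the calendar assessments during the hold and the end-of-treatment assessment. Confirmed responses stand.
- **Three PD visits inside the adverse event window are lost.** That holds only if the 70-day clock starts at the decision. From the last infusion it is about 1 or fewer, or at most 2 in the limiting case. Adverse events in the window are collected either way.

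No frequency can be given: Section 2.4.1 reports that albuminuria has occurred but gives no rate for a persistent ratio above 2000 mg/g. Reach is small, as the Amendment 3 rationale names two ongoing participants. If the affected participant is the last one on study, the Section 4.4 end-of-study definition closes follow-up anyway.

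**What to change.** 1. In the Table 5 spot urine cell, replace the withdrawal clause with an instruction to follow per Section 7.1. Keep the drug stop, the threshold and the follow-up to resolution.
2. In Section 4.1 and SAP Section 2.3, qualify the sentence on each participant's involvement so that those who stop treatment without progression stay in PD follow-up per Section 7.1. Without this, correcting Table 5 leaves a conflicting text in place.
3. Optionally, align the hepatotoxicity sentence in Section 2.4.1 with Section 7.1.1.1.

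The cost is one phrase in a table cell, one qualified sentence in each document and one optional risk-table sentence. No procedures are added, because the PD follow-up visits are already in the Schedule. The end-of-study definition and the timing of the final analysis do not change.
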